Title: Effect of health education on promoting influenza vaccination health literacy among primary school students: a cluster randomized controlled trial protocol

NCT number: NCT06048406

Document date: 01 September 2023

INTRODUCTION

The Influenza virus, known for its mutability and potent infectivity, poses a significant health risk. Recent trends indicate an escalating incidence of influenza in China, thereby posing a substantial threat to public health.^{1,2} According to national influenza surveillance data, each October marks the onset of the winter and spring influenza epidemic seasons across various regions in China.^{3,4} Currently, the most effective preventative measure against influenza is vaccination.⁵ Seasonal influenza vaccinations have demonstrated efficacy in reducing the risk of influenza infection and severe complications across all age groups.⁶ Seasonal influenza epidemics often precipitate outbreaks in densely populated areas such as schools, childcare institutions, and nursing homes.⁶

Health literacy, defined as an individual's capacity to acquire, comprehend, and utilize basic health information and services for informed health decisions, plays a pivotal role in vaccination uptake.^{7,8} Enhancing vaccine health literacy can potentially augment vaccination willingness and mitigate vaccination hesitancy.⁹ Therefore, improving the population's awareness, attitudes, and behaviors towards influenza vaccination health literacy is integral to the successful implementation of influenza

prevention and control measures and strategy development.

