While numerous studies have investigated the broader implications of health education interventions on vaccination awareness and rates, there remains a distinct lack of focused research specifically targeting primary school students, especially within the context of China.¹⁰⁻¹² The unique age group, characterized by their transitional cognitive abilities and susceptibility to influence, may respond differently to health literacy interventions than other age cohorts. Moreover, regional differences, cultural practices, and local health infrastructure in China might further impact the effectiveness of such interventions. Thus, this study aims to investigate the influence of health education on influenza vaccination rates and the level of influenza vaccination health literacy among fourth and fifth-grade primary school students. The methodological approach will involve a cluster randomized trial with schools serving as the unit of analysis. The findings will provide a scientific basis for future interventions.

METHODS AND ANALYSIS

Study objectives

This study seeks to explore the impact of health education interventions on vaccination and influenza vaccination awareness among senior primary school students. By evaluating the impact of health education on the seasonal influenza vaccination rate and the level of influenza vaccination health literacy, we aim to provide a scientific foundation for regional influenza prevention and control

strategies. The specific objectives of this research are: 1) To ascertain the rate of influenza infection, the status of influenza vaccination, and the level of health literacy related to influenza vaccination among primary school students in Dongguan City. 2) To compare and contrast the influenza vaccination rate and the level of influenza vaccination health literacy between the experimental and control groups, thereby evaluating the impact of health education intervention on these parameters. 3) To assess the efficacy of influenza vaccine immunization among primary school students in Dongguan City.

Study design

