The intervention group will receive a health education intervention focused on

influenza vaccination literacy, while the control group will continue with their standard school health education without any additional intervention. An influenza vaccination health education including topics such as the importance of influenza vaccination, benefits of vaccination, and vaccination methods, will be developed and reviewed by an expert group. The package for the intervention group will include educational activities, distribution of promotional materials, vaccination services, and distribution of vaccination souvenirs. The details are as follows:

1) Educational activities include classroom lectures and parent meetings. Medical professionals or public health experts will be invited to deliver lectures at the school, providing detailed information on the role and benefits of influenza vaccination and the risks of influenza. Teachers and relevant school staff will be trained to understand the importance of influenza vaccination, reinforcing these messages in everyday teaching. Content about influenza vaccines will be incorporated into school health education courses, facilitating student learning about influenza vaccines. In addition, Teachers will discuss the importance of the flu vaccine at parent meetings, encouraging parents to facilitate their children's vaccination.

2) Promotional materials include educational booklet, animated videos, vaccination service and vaccination souvenirs. Educational booklet will be designed and distribute to students to raise their awareness of flu vaccines. Animated videos will be created to explain the effects of flu vaccines and the benefits of vaccination in an easy-to-understand manner. These videos will be played on school TVs or computers, and students will be organized to watch them. Influenza vaccination services will be provided to students who have no contraindications to influenza vaccination, are in

good health, and are 4-6 months post their last influenza vaccination, based on the principle of informed consent, voluntariness, and self-payment. 'Epidemic Prevention Little Guards' medals will be created and distributed to vaccinated students as a commemorative incentive to encourage vaccination.

Intervention time

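### The vaccination-rate difference estimates the effect of a package (education, vaccination service and medal), not of health education as the aim and objective 2 state

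*Combined protocol and SAP*

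**What the plan says.** Under Intervention methods, the protocol defines what the intervention schools receive: "The package for the intervention group will include educational activities, distribution of promotional materials, vaccination services, and distribution of vaccination souvenirs". On the service it says: "Influenza vaccination services will be provided to students who have no contraindications to influenza vaccination". The offer is made "based on the principle of informed consent, voluntariness, and self-payment", and the text does not say where vaccination takes place. On the souvenirs it says: "medals will be created and distributed to vaccinated students as a commemorative incentive to encourage vaccination". For the comparison schools, "the control group will continue with their standard school health education without any additional intervention".

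The end of the Introduction and the opening of Study objectives state the aim as the influence of health education on the vaccination rate and on vaccination health literacy. Objective 2 compares the two arms on both and describes this as "evaluating the impact of health education intervention on these parameters". Study outcomes makes both of them primary, and Sampling method bases the sample size on vaccination rates of 80% and 50%.

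**The concern.** The contrast between arms is wider than the claim attached to it. A vaccination service may make vaccination easier to obtain, and the medal rewards the very event that the primary outcome counts. Either could raise uptake without any change in what families know or think about the vaccine. Under objective 2 as worded, the whole difference would still be reported as the impact of health education.

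This matters because Study objectives offers the results as a basis for regional influenza control strategy. A health department told that education raised uptake could fund lectures and booklets, leave out the service and the incentive, and not get the effect that the trial reported.

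**Working it through.** **1. What differs between the arms** (Intervention methods)

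| Component | Intervention | Control |
|---|---|---|
| Routine school health education | yes, with influenza vaccine content added | yes |
| Lectures, parent meetings, booklet, videos | yes | no |
| Vaccination service | yes | no |
| Medal for vaccinated pupils | yes | no |

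**2. What one contrast can identify.** Write the uptake difference as D = E + S, where E is the contribution of education and S is that of the service and medal together, including any interaction with education. The design gives one equation for two unknowns. The plan's own figure is D = 80 − 50 = 30 points. If a share s of it is due to the service and medal, then E = 30 × (1 − s):

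| s | 0 | 0.25 | 0.50 | 0.75 | 1 |
|---|---|---|---|---|---|
| E (points) | 30 | 22.5 | 15 | 7.5 | 0 |

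Nothing in the plan favours one column over another.

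**3. Whether other planned data close the gap**
- Design: there is no education-only arm, no service-and-medal arm and no factorial structure.
- Statistical analysis plan: it lists two-group tests and one logistic regression relating literacy to willingness to be vaccinated. There is no component or mediation analysis.
- Appendices I and II: both forms ask whether and when the child was vaccinated, and the parent form also asks why. Neither asks where, or through which service. Answer options are not printed, so it is unknown whether the reasons cover convenience or reward.
- Literacy as a fallback: Data collection and analysis places vaccination status in the behaviour dimension of literacy. The service and medal can therefore move part of the literacy score too.

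**4. Could the service and medal alone give a positive result?** This is an illustration, because the protocol states no intracluster correlation (ICC). Assumptions: education has no effect on uptake; the control rate is 50%; there are 10 schools per arm with 138 pupils each (Sampling method), so 1,380 per arm; the test is cluster-adjusted, two-sided at 0.05, with a normal approximation.

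Effective number per arm: n_e = 1380 / (1 + 137 × ICC).

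Power = Φ{[d − 1.96 √(2p̄(1 − p̄)/n_e)] / √([p₁(1 − p₁) + p₂(1 − p₂)]/n_e)}.

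Example: d = 0.15 and ICC = 0.05. Then n_e = 1380/7.85 = 175.8 and p̄ = 0.575. The two standard errors are √(0.48875/175.8) = 0.0527 and √(0.4775/175.8) = 0.0521. The argument of Φ is about 0.895, and the power is 0.82 (0.815 to three decimals).

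| Lift from service and medal | ICC 0.01 | 0.05 | 0.10 | 0.20 |
|---|---|---|---|---|
| 10 points | 0.93 | 0.47 | 0.28 | 0.17 |
| 15 points | >0.99 | 0.82 | 0.55 | 0.32 |
| 30 points | 1.00 | 1.00 | 0.99 | 0.89 |

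So over much of this range the trial could well show a significant uptake difference with no education effect at all. The table shows what is possible. It is not evidence about how large the lift will be.

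**The case against.** The best reply is that the protocol hides nothing. It lists all four components, and Intervention time calls the bundle a health education intervention package. Objective 2 can then be read as being about the package, and randomisation supports that estimate. This stands: the comparison is valid for the package. It does not settle the wording, because Intervention methods describes the intervention as focused on vaccination literacy and gives the educational content as topics to be taught. Supplying and rewarding vaccination are not topics of that kind, and the stated aim names health education alone.

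A second reply is that literacy is also primary and is measured before and after, so flat literacy beside higher uptake would be visible. That would be a useful warning sign, but it would not divide the uptake difference into parts.

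Some stronger readings are tempting, and the documents do not support them:
- *The title already credits education with uptake.* It reads "Effect of health education on promoting influenza vaccination health literacy among primary school students", which is a claim about literacy only.
- *Vaccination is given in school.* The protocol has disease-control staff visiting schools to deliver the package, but it gives no place for the vaccination service. In-school delivery is an inference.
- *The service directly produces the outcome.* It is voluntary and paid for by families, and the assumed 50% in controls shows that vaccination is expected without it. It may ease access; no price reduction is stated.
- *Recording where the child was vaccinated would isolate education.* Place is determined after randomisation, and education may be the reason a family used the service. Place also says nothing about the medal.

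**Conclusion.** The point holds as one of attribution, not of validity. The randomised uptake difference estimates the effect of education, vaccination service and incentive together. Describing it as the impact of health education goes beyond what the design can show. The education share of the assumed 30-point difference is unidentified between 0 and 30 points. That range assumes that no component lowers uptake, and it would apply to any bundle tested as a single contrast. It does not show that education is ineffective.

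The whole literacy score is not a clean outcome for education either, because it includes vaccination status. The knowledge and attitude items are closer to it, but they still compare arms that differ in the full package. Allocation and sample size are unaffected. The change is worth making because it alters what the trial may conclude.

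**What to change.** 1. Reword the aim in the Introduction and Study objectives, objective 2 and the planned uptake conclusion. For example: *to compare the influenza vaccination rate between schools allocated to a multicomponent package (education, vaccination service and incentive) and schools continuing routine health education*.
2. Confine claims about education as such to the knowledge and attitude items of the literacy scale, reported separately, with vaccination status left out. State beside them that the arms still differ in the whole package.
3. Optionally, add one follow-up item asking whether the child was vaccinated through the package service or elsewhere. Report it descriptively, and say that it does not isolate the effect of education.

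The title needs no change on this ground. The cost is a few sentences, a separate report of items already collected and, if wanted, one extra question. Delivery, allocation and sample size stay as they are. The downside is a narrower headline claim.

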Staff of the affiliated street Center for Disease Prevention and Control (CDC) will visit the school in the first month to implement intervention activities using the health education intervention package. The intervention period will commence in September 2023 and conclude in February 2024, resulting in a total intervention duration of approximately three to four months. The specific intervention process is as follows: 1) At the start of the semester (early intervention stage in September 2023), initiation activities will be conducted. The investigators will introduce the study to teachers and students, and medical professionals or public health experts will be invited to deliver classroom lectures at the intervention group schools. Baseline data will be collected at this stage. 2) During the intervention period (September 2023 – January 2024), the intervention group will follow the health education intervention toolkit to conduct intervention activities. 3) At the conclusion of the semester (February 2024), follow-up data will be collected. The intervention timeline is shown in the Figure 2.

Data collection and analysis

Questionnaire surveys will be administered to students and parents before and after

the intervention, using self-completion. The questionnaire design, which is informed by similar research literature (Appendix 1 & 2), will undergo evaluations for reliability and validity. The questionnaire will include the following content: 1) Socio-demographic characteristics (name, age, sex, class, residential address, parents' educational level, occupation, family income); 2) Personal history (basic disease history, allergy history, and personal history); 3) Influenza vaccination health literacy level. The health literacy level concerning influenza vaccination will be assessed across four dimensions: knowledge, attitude, behavior, and skills related to influenza vaccination. Details of these four dimensions include knowledge of basic facts about the influenza vaccine (such as its efficacy, vaccination frequency, and side effects), attitudes towards the influenza vaccine (including perceptions of its efficacy and safety), behavioral characteristics related to influenza vaccination (such as willingness to be vaccinated, vaccination status, and timing of vaccination), and sources of information about the influenza vaccine.

Confirmation of influenza and surveillance of influenza-like cases

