Primary outcomes include the influenza vaccination rate and the influenza vaccination health literacy level. The influenza vaccination rate will be calculated as the number of vaccinated individuals divided by the total number of individuals, multiplied by 100%. Regarding the influenza vaccination health literacy level, each correct answer for the scale will be scored as one point, with incorrect answers receiving no points. Based on the scores, health literacy levels will be categorized as low, medium, or

high.

Secondary outcomes include influenza incidence, the ILI incidence and the influenza vaccine protection rate. The influenza incidence will be calculated as the number of individuals diagnosed with influenza divided by the total number of individuals, multiplied by 100%, The ILI incidence will be calculated as the number of ILI cases divided by the total number of participants, multiplied by 100%. The influenza vaccine protection rate will be calculated as the difference between the incidence rate in unvaccinated individuals and the incidence rate in vaccinated individuals, divided by the incidence rate in unvaccinated individuals, multiplied by 100%.

Statistical analysis plan

Continuous variables will be described using means \pm standard deviation or median (interquartile range), and comparisons will be made using two independent samples t-tests or Wilcoxon rank-sum tests. Categorical variables will be described using frequency and composition ratios, and rate comparisons will be conducted using Chi-square tests or Fisher's exact probability method. The association between the level of influenza vaccination health literacy and vaccination willingness will be analyzed using multivariate logistic regression.

Quality control

Quality Control will be conducted in accordance with the requisite quality control standards, with dedicated on-site quality control personnel assigned to oversee investigation and evaluation. These personnel should be proficient in various testing technical requirements and quality control points, and familiar with the on-site

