Do you think the flu vaccine needs to be given every year to

prevent the flu?

Do you think getting a flu vaccine is good for you and your child's health?

Do you think it is necessary to get a flu vaccine?

Are you confident that the flu vaccine is safe?

Behavioral questions

Within the last year, have you ever had influenza (or had a sudden onset of illness with a high fever $\geq 38^{\circ}\text{C}$ accompanied by flu-like symptoms such as generalised malaise, myalgia, sore throat, etc.)?

If yes, when was the last time you had influenza (or had a sudden onset of illness with high fever $\geq 38^{\circ}\text{C}$ accompanied by influenza-like symptoms such as generalised malaise, myalgia, sore throat, etc.)?

Has your child had influenza (or had a sudden onset of illness with high fever $\geq 38^{\circ}\text{C}$, accompanied by flu-like symptoms such as generalised weakness, myalgia, sore throat, etc.) within the last year?

If yes, when was the last time your child had influenza (or had a sudden onset of illness with a high fever $\geq 38^{\circ}\text{C}$ accompanied by influenza-like symptoms such as generalised malaise, myalgia and sore throat)?

Have you taken your child for a flu vaccination between 2020 and 2022?

Have you or your spouse been vaccinated against flu in 2023?

If you have been vaccinated against flu, when did you or your spouse get the flu vaccine this year?

Has your child been vaccinated against flu in 2023?

If your child has been vaccinated against flu, when did your

child get the flu vaccine this year?

If your child has been vaccinated against flu, why did you decide to take your child for a flu vaccination this year?

If your child hasn't been vaccinated against flu, why did you decide not to take your child for a flu vaccination this year?

If your child has not had a flu vaccination this year, are you currently willing to take your child to get one?

Would you be willing to take your child for a flu vaccination in the future?

Would you like to recommend that others get the flu vaccine?

Skill Questions

Do you know how to schedule your flu vaccine?

Do you take an active interest in information about flu vaccinations?

Where do you get information about flu vaccinations?

Appendix II Questionnaire for Health Literacy Study of Influenza Vaccination among Primary School Students in Dongguan City (Student Version)

Question

Basic information

Your class?

Your gender?

How old are you?

knowledge questions

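### As written, the school vaccination service admits only children 4 to 6 months after their last dose, which shuts out every child last vaccinated before March 2023 and, on the plain wording, never-vaccinated children

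*Combined protocol and SAP*

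**What the plan says.** Intervention methods, item 2, sets the conditions for the school vaccination service, which is offered in the intervention arm only. Children must have no contraindications, be in good health, and be such that they "are 4-6 months post their last influenza vaccination". The conditions are cumulative. Nothing marks the interval as a minimum, and no clause covers a child with no previous dose. The same item describes a medal for vaccinated students as a "commemorative incentive to encourage vaccination".

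Intervention time gives the dates of the activities: "During the intervention period (September 2023 – January 2024"). Follow-up data are collected in February 2024.

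Study outcomes makes the vaccination rate a primary outcome: "The influenza vaccination rate will be calculated as the number of vaccinated individuals divided by the total number of individuals". It states no period over which vaccinations are counted.

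Other places bear on how the interval should be read:

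- The Introduction says that "each October marks the onset of the winter and spring influenza epidemic seasons".
- The parent questionnaire (Appendix I) has an attitude item beginning "Do you think the flu vaccine needs to be given every year to" and a behaviour item asking "Have you taken your child for a flu vaccination between 2020 and 2022".
- Study sample excludes from the trial children who were vaccinated recently, without defining how recently.

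**The concern.** A rule on the time since a previous vaccination normally protects against doses given too close together, so it needs a lower limit. This one also has an upper limit of six months. Influenza vaccination is seasonal, and a child vaccinated once a year is about 12 months past the last dose when the next is due, six months beyond the limit. Taken literally, the service turns away children last vaccinated in earlier seasons and, on the plain wording, children who have never been vaccinated. A programme to raise coverage would want to reach both groups.

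Two things are at stake. If staff follow the sentence, a component of the intervention aimed at a primary outcome misses much of its natural target. If those running the service in the ten intervention schools (five in each of two districts) read it differently, the arm does not receive one intervention.

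**Working it through.** The plan gives no figure on this point to reproduce, so the check is calendar arithmetic.

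**Inputs.** The interval is 4 to 6 months (Intervention methods). Activities run from September 2023 to January 2024 (Intervention time). I take 1 September 2023 and 31 January 2024 as the outer limits, which is the most lenient choice.

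**Formula.** On service date *t*, a last dose qualifies if it falls between *t* − 6 months and *t* − 4 months.

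| Service date | Earliest qualifying last dose | Latest qualifying last dose |
|---|---|---|
| 1 Sep 2023 | 1 Mar 2023 | 1 May 2023 |
| 30 Sep 2023 | 30 Mar 2023 | 30 May 2023 |
| 31 Oct 2023 | 30 Apr 2023 | 30 Jun 2023 |
| 30 Nov 2023 | 30 May 2023 | 30 Jul 2023 |
| 31 Dec 2023 | 30 Jun 2023 | 31 Aug 2023 |
| 31 Jan 2024 | 31 Jul 2023 | 30 Sep 2023 |

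Over the whole period the admitted last-dose dates are 1 March to 30 September 2023. If the service is given only in September, when CDC staff are due to visit, they are 1 March to 30 May 2023. The early cut-off only moves later as the period runs, so a child outside it on 1 September 2023 never comes back in. Extending the service to 29 February 2024 would move the late end to 29 October 2023 and leave the early cut-off unchanged.

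**Example children.**

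- Dose on 28 February 2023: 6 months 4 days old on 1 September 2023, already outside.
- Dose on 31 December 2022: 6 months reached on 30 June 2023; 8 months 1 day old on 1 September 2023 and 13 months old on 31 January 2024.
- Dose on 1 October 2022, at the onset of the previous season: 6 months reached on 1 April 2023; 11 months old on 1 September 2023 and 15 months 30 days old on 31 January 2024.

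Every dose in 2020–2022, the years the parent form asks about, is therefore outside.

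**Alternative readings.**

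1. *A spacing rule that applies only to previously vaccinated children.* Never-vaccinated children are then admitted. The six-month upper limit still bars everyone last vaccinated before March 2023.
2. *A minimum interval expressed as a range.* On 1 September 2023, a 4-month minimum admits doses up to 1 May 2023 and a 6-month minimum admits doses up to 1 March 2023. Both dates are later than 31 December 2022, so either choice admits every child last dosed in 2022 or earlier from the first day. A range is still not a usable minimum: a child dosed between 2 March and 1 May 2023 passes one and fails the other.

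**A consequence of the plain wording.** All admitted last-dose dates lie in 2023. Every child admitted would already answer yes to the questionnaire item on influenza vaccination in 2023. If that item alone supplied the primary rate, which the protocol does not say, the service could not turn any no into a yes.

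**The case against.** The strongest reply is that this is a drafting slip that nobody would apply literally. The phrase follows two pre-vaccination safety checks, where a time since last dose reads naturally as a spacing precaution. The trial's exclusion of recently vaccinated children points the same way: the stated worry is a dose given too recently. The sample-size section anticipates 80% vaccinated in the intervention group, which fits poorly with a service closed to unvaccinated children. A condition on a child's last vaccination can also fairly be read as not applying to a child who has had none. All of this makes a minimum interval the likely intent. None of it removes the upper limit from the text or says which minimum applies.

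Several other points stand and limit the concern:

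- The service is one voluntary, self-paid part of a package that also has lectures, parent meetings, booklets and videos.
- Vaccination elsewhere remains possible, and the primary rate as defined does not depend on where the dose was given. The medals go to vaccinated students generally, so the interval rule does not restrict them.
- The questionnaire covers "vaccination status, and timing of vaccination", so doses could be dated at analysis.
- The evidence for a yearly schedule is a questionnaire item, not a protocol statement.
- How staff would act on the sentence is not documented.
- Because of the recent-vaccination exclusion, the late end of the window may be narrower for enrolled children than the table shows. That exclusion brings no one in at the early end.

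**Conclusion.** The concern holds: the rule is wrong as written. Any child last vaccinated before 1 March 2023 is outside the service window throughout, and this is true on the plain wording and on the spacing reading alike. The exclusion of never-vaccinated children follows from the plain wording only. The date result assumes that service days fall from 1 September 2023 onward; a later start shuts out more children.

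The number of children affected and the effect on the primary vaccination rate cannot be derived. The documents give no vaccination-history figures and no counting period for the rate, and other routes to vaccination stay open. The rule does not by itself make the assumed 80% unattainable, and no sample-size figure depends on it. My confidence is moderate, because the authors probably meant a minimum interval and staff may have read it so. It should still be corrected, since it is the only interval rule stated for the service.

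**What to change.** In Intervention methods, item 2, replace the closed window with one minimum interval since any previous influenza vaccine dose. The investigators should choose the value and state it as a single number. Add that never-vaccinated children, and children vaccinated only in earlier seasons, are eligible if they meet the health and contraindication conditions.

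This costs one sentence, to be settled before the service starts. It needs no change to sample size, schedule or data collection.
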